10.10. Dose Modification

If a subject refuses to have a study medication treatment, the investigator must report the visit number, visit date, and state the reason the subject refused to allow treatment in the subject's CRF.

If the subject's refusal is associated with an AE, the investigator must also report the event on the appropriate CRF.

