### 2. STUDY DESIGN

This is a Phase 3, open-label, long-term safety study of A-101 45% Topical Solution in subjects with common warts.

In order to be eligible for A-101-WART-303, subjects must have completed protocol treatment on either the A-101-WART-301 or A-101-WART-302 study.

Subjects that have complete clearance of all warts at the end of A-101-WART-301 or A-101-WART 302 may enter into the A-101-WART-303 study following completion of the Visit 1 assessments. These subjects will be followed every 6 weeks to assess for a recurrence or development of new common warts. If a recurrence occurs or a new wart develops these subjects may return to the investigational site to receive A-101 45% Topical Solution twice a week for an additional 8 weeks.

Subjects that have warts that have not cleared (or were not treated) at the completion of A-101WART-301 or A-101-WART-302 may enter into the A-101-WART-303 study following completion of the Visit 1 assessments will receive A-101 45% Topical Solution twice a week for 8 weeks.

Subjects may continue to receive A-101 45% Topical Solution twice a week for 8 weeks if their warts are not clear at the end of the 8-week treatment period but the 8 weekly treatments must be initiated by Day 122.

[figure not shown]
Visit 1 of A-101-WART-303 can be the same day as Visit 13 of either A-101-WART-301 or A101-WART-302.

All subjects will be required to remain on study for a total of 6 months.

During the study, the investigator may identify from 1 to 6 common warts to be treated twice a week for up to 8 weeks (maximum of 16 treatment applications). An 8-week treatment course may be repeated.

[Figure 1](#) below provides a graphical representation for treatment in this study.

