### 3.3 Study Day and Period Study Day

As shown in [Figure 1](#), subjects can potentially take multiple courses of treatment throughout the study. Subjects entering the study with warts will receive treatment at study entry as shown in [Table 2](#). Subjects who enter without any common warts do not receive study medication immediately and follow visit schedules shown in [Table 3](#). If these subjects develop any wart during the study, they will then begin a treatment regimen and follow the visit schedule for treated subjects. Subjects can initiate a treatment regimen up to three times (cycles) throughout the course of the study up to day 122. To allow for comparisons referencing each treatment cycle, Study Day will be calculated in two ways. Study day is defined as the relative day in the study from time of enrollment (first dose if treated immediately). Period study day is defined as the relative day from the day of first dose within a treatment cycle.

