### 3.5 Subject Enrollment and Disposition

The number of subjects enrolled to this study and their prior participation in double-blind studies will be presented by treatment status and double-blind treatment assignment. Study completion status and the reasons for discontinuation by major reason (lost to follow-up, adverse event, poor compliance etc.) will be presented for both All Enrolled Population and Safety Population by treatment group as defined in [Section 3.2](#).

A listing will be provided of all subjects discontinued from the study after enrollment, broken down by previous double-blind study participated and study center, giving a subject identifier and the specific reason for discontinuation, and the duration of treatment before discontinuation.

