### **3.11.2 Adverse Events**

Adverse events are coded using the MedDRA (Version 22) and are categorized by system organ class (SOC) and preferred term (PT). Only treatment emergent adverse events are included in summary tabulations (i.e. adverse events occurring within 30 days of each application of study medication). All adverse events are included in the data listings including those that are not considered treatment emergent.

To allow differentiation as to which study period an Adverse Event occurred, three categories are defined based upon onset date. Adverse Events that had onset dates prior to the first application of study medication are considered "prior". Adverse events with onset dates on or within 30 days of an application of study medication are considered "treatment emergent". Events with onset dates more than 30 days after the most recent application of study medication are considered as "post-therapy." In this study, subjects can possibly receive medication up to three cycles and multiple doses of medication within a treatment cycle. The above rule will be applied to all known doses of medication while determining study period.

Frequency tabulations are presented by MedDRA SOC and preferred term, for all adverse events; study treatment-related adverse events, adverse events resulting in discontinuation of study treatment, serious adverse events and adverse events by maximum severity. Adverse events resulting in discontinuation are those with 'action taken' recorded as 'drug withdrawn'.

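### An AE that leads a subject to decline a further course can be left out of the AE-discontinuation table, because SAP 3.11.2 counts only 'drug withdrawn'

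*SAP*

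**What the plan says.** SAP 3.11.2 plans frequency tables that include "adverse events resulting in discontinuation of study treatment, serious adverse events and adverse events by maximum severity". The discontinuation table is filled by one rule: "Adverse events resulting in discontinuation are those with 'action taken' recorded as 'drug withdrawn".

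The treatment it describes is intermittent. SAP 3.3: "Subjects can initiate a treatment regimen up to three times (cycles) throughout the course of the study up to day 122". A repeat course is permitted, not required. SAP 2: "Subjects may continue to receive A-101 45% Topical Solution twice a week for 8 weeks if their warts are not clear". Follow-up does not end when treatment does. SAP 2 again: "All subjects will be required to remain on study for a total of 6 months".

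Protocol 10.10 collects refusals: "If a subject refuses to have a study medication treatment, the investigator must report the visit number, visit date, and state the reason". It adds that, if the subject's "refusal is associated with an AE, the investigator must also report the event on the appropriate CRF".

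Disposition in SAP 3.5 covers study completion status and "the reasons for discontinuation by major reason (lost to follow-up, adverse event, poor compliance etc".

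**The concern.** The drug-withdrawn action code suits continuous treatment, where stopping is an event that happens to ongoing drug. Here much of the stopping can take place between courses. A subject finishes the scheduled applications, still has warts or develops new ones, and declines the next course because of a reaction. No treatment is running at that moment, so the site may not record the AE as having led to drug withdrawal. The subject stays on study and can be counted as a completer.

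The primary objective is long-term safety, and the sample size is built on at least 100 subjects requiring repeated treatment. Whether a reaction made subjects unwilling to repeat treatment is therefore central tolerability information, and the AE-discontinuation table is where a reader would look for it. The point also affects how the by-cycle local skin reaction summaries in SAP 3.11.3 are read. Cycles 2 and 3 contain only subjects who started them, so without the number who declined because of a reaction a reader cannot judge whether later cycles look mild because less tolerant subjects had stopped.

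**Working it through.** Most of this check sets passages side by side; the arithmetic only illustrates size.

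**1. Is there a point at which treatment can stop with no drug running?** The last scheduled application is on Day 53 (Protocol 10.5). Drug for a new course is dispensed at Visit 5, Day 60, to subjects with uncleared or new warts (Protocol Table 2, footnote 6). That leaves 60 − 53 = 7 days with no scheduled application before the decision. If a second course starts on Day 60 and follows the same schedule, its Visit 5 falls on study Day 60 + 59 = 119, inside the Day 122 limit for starting a course. Three courses therefore give up to two such decision points.

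**2. Where would a subject who declines at Day 60 because of an AE appear?**
- AE-discontinuation table: only if the site entered drug withdrawn. Neither document lists the action-taken options or says how a decision between courses is coded.
- Other AE tables: yes, if onset is within 30 days of an application. After a Day 53 application that window runs to Day 53 + 30 = Day 83. All AEs are also listed.
- Disposition (SAP 3.5): AE appears as a reason only if the subject leaves the study.
- Compliance (SAP 3.11.1): calculated only up to the last application, so not starting another course does not lower it.
- Protocol 10.10 refusal record: no SAP table or listing uses it.

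The event is kept. Its link to stopping treatment may not be.

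**3. The plan's own figure.** SAP 3.13 and Protocol 14.1 give 400 subjects, 200 previously on active treatment, and 26% clearance: 200 × (1 − 0.26) = 148, which reproduces. This is a minimum from prior-active subjects; treated subjects who previously received vehicle would add to it.

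**4. Illustration of size.** Let N be treated subjects, w the proportion withdrawn during a course (all coded drug withdrawn), r the proportion who decline a further course because of an AE, and m the share of those refusals not coded drug withdrawn. Then

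- rate shown = w + r(1 − m)
- rate with refusals counted = w + r
- subjects absent from the table = N × r × m

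The documents give none of w, r or m. Assuming r = 1% to 5%:

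| N | m | Absent at r = 1% | Absent at r = 5% |
|---|---|---|---|
| 148 | 1 | 148 × 0.01 = 1.5 | 148 × 0.05 = 7.4 |
| 148 | 0.5 | 0.7 | 3.7 |
| 148 | 0 | 0 | 0 |
| 100 | 1 | 1 | 5 |

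With w = 2%, r = 5% and m = 1, the table would show 2.0% against 7.0% with refusals counted.

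**The case against.** The strongest reply is that nothing shows these cases will be lost. Protocol 7.3 lists an unacceptable AE as a reason for removal from study therapy. Protocol 13.2.3 allows withdrawal from study drug for an AE at any time, with the AE and termination pages completed. A site could code drug withdrawn for an AE that ends further treatment, and SAP 3.11 places additional data-handling rules in a separate document that is not available here. This stands. A reader might infer that AE-driven refusals between courses are necessarily missed and that the reported rate is too low; the documents support only that they can be missed. The same uncertainty means that sites may code one decision in different ways.

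A reader might also extend the point to applications refused within a course. That does not follow: drug is then in use, a mid-course stop for an AE is what the code records, and one skipped application is not discontinuation.

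Protocol 10.10 speaks of refusing a treatment, recorded by visit, and does not clearly cover declining an optional course. This also stands. The reason for not starting a course may not have been collected uniformly.

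Finally, much is already planned: AEs in the other tables, local skin reactions by cycle, and clearance by cycle, so subjects not clear at the end of one cycle can be compared with those entering the next. That gives a rough count of who did not continue, but not the reason.

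**Conclusion.** The gap is real but limited. The rule in SAP 3.11.2 can omit an AE that led a subject with uncleared or new warts to decline a further course, and no other planned summary restores that link. The AE is not lost from the listings or, if treatment emergent, from the other AE tables. Sample size and efficacy results are unaffected, and the table carries no threshold or test.

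The size cannot be determined from the documents. It is zero if every such case is coded drug withdrawn; otherwise it depends on a decline rate that is not given. The 1.5 to 7.4 subjects in the illustration rest on assumed decline rates of 1% to 5%, no such case coded drug withdrawn, and 148 treated subjects.

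A reader might try to sharpen this by applying 74% to the 148 to count candidates for a second course (148 × 0.74 = 109.5, about 110). The documents do not support that step: the 26% is a proportion of warts clear at the end of the parent studies, not of subjects clear after a course in this one.

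The change is still worth making. It replaces a stated rule with one that suits repeat courses, in a table that serves the primary objective, and relies largely on data already required.

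**What to change.** In SAP 3.11.2, count an AE as leading to discontinuation of study treatment if any of these holds:

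- (a) action taken is drug withdrawn;
- (b) it is the recorded reason for a Protocol 10.10 refusal, including refusal of a further course, in a subject who still has uncleared or new warts and has no later application;
- (c) it is the reason for leaving the study on the disposition record.

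The wart condition in (b) keeps out a subject who skips the Day 53 application for a mild AE and is clear at Day 60. Criterion (c) overlaps with SAP 3.5, but makes the AE table agree with disposition.

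State that Protocol 10.10 refusals include declining a further course.

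In SAP 3.5 add, by cycle: the number with uncleared or new warts who could start a further course by Day 122, the number who started, and the number who did not, with the recorded reason where available.

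The cost is one definition, one clarifying sentence and one table. Dosing, visits and sample size do not change. The reported discontinuation rate may rise, and reasons may be incomplete where sites did not treat a declined course as a 10.10 refusal.

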### **3.11.3 Local Skin Reactions**

The number of subjects with local skin reaction signs or symptoms that worsened by at least 1 grade from baseline any time after the first application of study medication will be tabulated by treatment group for each LSR as well any LSR. A separate summary limited to LSRs that worsen and which occur within 30 days of the last application of study medication will be provided. Additionally, to assess effect of number of cycles of applications of study medication on LSR, this summary will be presented by treatment cycle also.

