12.1. Local Skin Reactions (LSRs)

The LSR assessment is the Investigator's assessment of the signs and the subject's assessment of the symptoms associated with irritation at the identified common wart site (*i.e.*, the common wart and the skin immediately surrounding the common wart exposed to study medication).

The Local Skin Reaction signs to be assessed are:

- Erythema
- Edema
- Erosion
- Ulceration
- Vesicles/bullae
- Excoriations
- Scabbing

The Local Skin Reaction symptoms to be assessed (by the Subject) are:

- Stinging/burning
- Pruritus (itch)

The Investigator will evaluate the LSR signs at the each identified common wart site as follows:

- At visits where a study medication treatment or retreatment is performed:
 - Perform an LSR assessment prior to any study medication application
 - and

The Subject will assess the LSR symptoms at the identified common wart site as follows:

- At visits where a study medication treatment or retreatment is performed:
 - Perform an LSR assessment prior to any study medication application

At visits where **NO** study medication treatment is performed:

- Perform an LSR assessment.

Subjects are to remain in the clinic for 20 minutes after the application of their study medication. Any local skin reactions or other adverse experiences that occur during this time period must be

Aclaris Therapeutics, Inc.

Protocol Number: A-101-WART-303

Protocol Version 3: 14 February 2019

documented as an adverse event.

The Investigator and Subject should report the one integer that best describes the severity of each LSR sign or LSR symptom for the common wart site using the scale below:

Local Skin Reactions	
Grade	Descriptor
0	None OR No signs or symptoms present.
1	Asymptomatic or mild symptoms OR clinical or diagnostic observations only OR intervention not indicated.
2	Moderate OR minimal, local or noninvasive intervention indicated.
3	Severe or medically significant but not immediately life threatening OR disabling OR limiting self-care of activities of daily living.

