14.4. Statistical Analysis of Safety Data

Unless otherwise stated, all safety summaries will be conducted using the ITT population. All safety summaries will be produced for the following groups:

- Subjects treated in the study that were randomized to active treatment during the previous A101-WART 301/302 study.
- Subjects treated in the study that were randomized to vehicle during the previous A101-WART 301/302 study.
- Subjects treated in the study overall.
- Subjects not requiring treatment during the study that were randomized to active treatment during the previous A101-WART 301/302 study.
- Subjects not requiring treatment during the study that were randomized to vehicle during the previous A101-WART 301/302 study.
- Subjects receiving active treatment during the study or the previous A101-WART 301/302 study.

The proportion of subjects with treatment emergent adverse events will be tabulated and presented by System Organ Class and Preferred Term from the Medical Dictionary for Regulatory Activities (MedDRA). Likewise, the proportion of subjects with serious AEs will be summarized. Adverse event summaries will be presented showing the proportion of subjects experiencing adverse events, both overall and by MedDRA System Organ Class. The version of MedDRA to be used for the analysis of this study will be specified in the SAP.

Aclaris Therapeutics, Inc.

Protocol Number: A-101-WART-303

Protocol Version 3: 14 February 2019

Local skin reaction (LSR) scores and clinically relevant abnormal laboratory results will be tabulated and presented at the subject level. For each LSR sign and at each in-house visit, the proportion of subjects who had at least one treated wart with LSR severity ≥ 1 will be summarized.

Safety summaries will be supported by listings of all adverse events, laboratory results, and LSR data.

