### **3.11.1 Extent of Exposure**

The duration of treatment, the number of application days (i.e. the actual count of days where an application occurred), the mean applications per wart (for each subject the sum of all applications across all treated warts and all application days divided by the total number of treatments for all treated warts), and the total applications will be summarized using descriptive statistics (n, mean, SD, median, minimum and maximum). The percentage of total wart treatments that were performed in 1, 2 or 3 applications is also provided.

Overall compliance is calculated as the total number of wart treatments performed during the treatment period (through date of last application to any wart) divided by the total number of wart treatments expected to be performed. The total number of warts treated is the sum of the retreatment and home application diary records completed times the number of warts assessed at baseline minus the number of warts scored as PWA=0 or having an LSR grade 3 at the most recent assessment (<= the date of the application).

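### No local skin reaction summary in SAP 3.11.3 separates grades 1, 2 and 3, and the protocol's subject-level tabulation of scores is not carried forward

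*SAP*

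**What the plan says.** Protocol 12.1 has seven signs and two symptoms scored at each identified wart site on an integer scale from 0 to 3. Grade 1 is "Asymptomatic or mild symptoms OR clinical or diagnostic observations only OR intervention not indicated". Grade 3 is "Severe or medically significant but not immediately life threatening OR disabling OR limiting self-care of activities of daily living".

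SAP 3.11.3 plans three summaries of these scores, for each LSR and for any LSR:

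- subjects with "signs or symptoms that worsened by at least 1 grade from baseline", at any point once treatment has begun;
- "A separate summary limited to LSRs that worsen and which occur within 30 days of the last application" of study medication;
- a repeat by cycle, to look at the effect of the number of cycles: "this summary will be presented by treatment cycle also".

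Protocol 14.4 plans two things. LSR scores are to be tabulated at the subject level, in a format it does not describe. In addition, for each sign at each in-house visit, it plans "the proportion of subjects who had at least one treated wart with LSR severity" of at least 1. It also promises listings of LSR data.

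SAP 3.14 records one change from the protocol, the analysis population. It does not mention the LSR tabulation.

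**The concern.** Long-term safety is the primary objective, and the product is applied repeatedly to the same skin sites. For that purpose it matters how severe local reactions become as well as how many subjects have one. The by-cycle table is the SAP's tool for seeing whether repeated courses make reactions worse, yet it records only whether a subject worsened.

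The SAP treats grade elsewhere as informative. In the compliance calculation, SAP 3.11.1 subtracts warts "having an LSR grade 3 at the most recent assessment" from the number counted. SAP 3.11.4 gives laboratory values a shift table to the worst post-baseline category. No planned SAP table says how many subjects reached LSR grade 2 or grade 3.

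**Working it through.** **1. What the rule counts.** The scale is 0, 1, 2, 3 (Protocol 12.1) and the rule is post-baseline grade minus baseline grade of at least 1 (SAP 3.11.3). The upward changes are 0→1, 0→2, 0→3, 1→2, 1→3 and 2→3. All six count as one identical event. One of them ends at grade 1, two at grade 2 and three at grade 3. The 30-day summary speaks only of LSRs that worsen, but on an integer scale any worsening is at least 1 grade, so its cut is the same. The by-cycle summary repeats the count.

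**2. A denominator for illustration.** The documents give no LSR rates. The nearest planned figure is the number of previously active-treated subjects expected to need treatment (Protocol 14.1, SAP 3.13): 200 × (1 − 0.26) = 148, which reproduces the stated 148. It is borrowed here only as a convenient denominator.

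**3. Three assumed severity mixes.** Assume 148 subjects, all at baseline grade 0, of whom 74 react on a given sign. Only the split of maximum grade differs between rows.

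| Maximum grade 1 / 2 / 3 | SAP count (worse by ≥1) | Protocol cut (severity ≥1) | Grade ≥2 | Grade 3 |
|---|---|---|---|---|
| 74 / 0 / 0 | 74/148 = 50% | 74/148 = 50% | 0 | 0 |
| 44 / 22 / 8 | 74/148 = 50% | 74/148 = 50% | 22 + 8 = 30 | 8 |
| 0 / 0 / 74 | 74/148 = 50% | 74/148 = 50% | 74 | 74 |

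Neither rule distinguishes the rows; a table of maximum grade does. If the first two rows were cycles 1 and 2 of the same subjects, the by-cycle table would read 50% and 50% while grade 3 went from 0 to 8.

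**4. Other planned outputs, set against the gap.**

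- *Protocol 14.4 by-visit proportion.* This is also a single cut, at severity 1, and it covers signs but not the two symptoms.
- *Protocol 14.4 subject-level tabulation.* It could carry grades, but its format is not given, SAP 3.11.3 does not include it, and SAP 3.14 does not withdraw it.
- *Adverse event table by maximum severity (SAP 3.11.2).* It uses the mild, moderate and severe definitions of Protocol 13.1.4, which differ from the LSR grades. Protocol 12.1 requires adverse event recording of reactions seen in the 20 minutes after an in-clinic application. In-office applications fall on Day 1 and Day 29 (Protocol 10.5), which is 2 of 16 per course. Other local reactions can be recorded as adverse events, but nothing requires a scheduled LSR grade to become one. SAP 3.11.2 plans no adverse event table by cycle.
- *Listings.* They hold the individual grades but do not summarise them by group or cycle.

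**The case against.** The strongest case against the point is that severity information is not absent from the plan, and much of that case stands. A reader might infer three stronger conclusions that the documents do not support.

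First, that the SAP 3.11.3 counts are the only LSR summaries planned, or that the safety outputs cannot show severity at all. Protocol 14.4 plans a by-visit proportion and a tabulation of scores, LSR data are to be listed, and reactions recorded as adverse events are tabulated by maximum severity. The gap lies in what the SAP specifies.

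Second, that Protocol 12.1 confines adverse event recording of local reactions to the 20-minute window. It makes recording mandatory in that window and exempts nothing else. Protocol 13.1.1 defines adverse events broadly enough to cover a severe wart-site reaction, 13.1.3 runs non-serious reporting from first treatment to last visit, and 13.2.1 has events elicited at every post-enrollment visit. What remains is that this route relies on non-directive questioning and another scale, so it does not replace systematic grades.

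Third, that most subjects will reach grade 1, leaving the count near its ceiling. No LSR rate is given. At Day 29 scores are taken before the in-office application, so the previous scheduled dose is Day 25, 4 days earlier. At Day 60 the previous scheduled dose is Day 53, 7 days earlier. Nothing in the documents shows such scores would be near a ceiling, and the point does not need it.

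It is also fair that worsening from baseline is a legitimate incidence measure in a descriptive single-arm study, and that it should be kept. If greater severity also brought new reactors, the present count would rise. It is blind only to severity among subjects already counted.

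**Conclusion.** The point holds as a gap in the SAP. All three summaries in SAP 3.11.3 rest on one yes/no count that gives mild and severe reactions equal weight, and the protocol's tabulation of scores has dropped out without being listed as a change. A rise in severity across cycles among the same reactors would not appear in any LSR summary the SAP plans, and the listings and adverse event tables fill the gap only in part.

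That follows from the rule itself and needs no assumption about reaction rates. How much would be hidden cannot be estimated from the documents: the 148, 74 and grade splits above are assumptions for illustration. No hypothesis test or sample size figure is affected. The change is worth making because it costs little and serves the primary objective.

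**What to change.** In SAP 3.11.3, tabulate each LSR sign and symptom by the subject's maximum post-baseline grade (0, 1, 2, 3) over all treated warts, by treatment group and by treatment cycle. A shift from baseline grade to maximum grade would serve equally well. Add one line for any LSR of grade 3. Keep the count of worsening by at least 1 grade alongside.

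State in the SAP that this table delivers the subject-level tabulation promised in Protocol 14.4, or record in SAP 3.14 that the tabulation is dropped and why. If the shift version is chosen, name the baseline used within a cycle, since SAP 3.4 gives a cycle-specific baseline and SAP 3.11 defines LSR baseline as before first application in this study.

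The cost is SAP wording and one larger table shell. The grades are already collected, so neither a protocol amendment nor new data are needed.
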